1.0 BACKGROUND AND RATIONALE

1.1 Study Synopsis

This is an exploratory (n=10-12 evaluable patients), open-label, single-arm, phase II study in patients with ‘non-inflamed’ unresectable regional or distant metastatic melanomas irrespective of prior treatment with PD-1/PD-L1 pathway inhibitors. The primary endpoint is to assess the incidence of histopathologic conversion of non-inflamed melanomas from patients with metastatic melanoma to ‘inflamed’ melanoma following single-agent entinostat “priming” (entinostat monotherapy). More specifically, patients with metastatic melanomas that have no evidence of tumor-infiltrating or tumor-associated lymphocytes (TIL/TAL), based on standard hematoxylin and eosin (H&E) staining of representative tumor sections (non-inflamed melanomas) will receive weekly entinostat for 3 weeks in cycle 1 (entinostat monotherapy; 5mg PO, qwk on D1, D8, D15 of cycle 1; cycle length = 21 days). Mandatory tumor tissue biopsies will be performed in the end of cycle 1, beginning of cycle 2 (day 22±2 days), immediately before treatment with concurrent entinostat (once weekly × 3) and pembrolizumab (200 mg q3wks) in cycles 2-9 (see section 5.2.1 drug dosing schema). Correlative studies will be performed at baseline and in the end of cycle 1, beginning of cycle 2 (day 22±2 days) to assess whether: (a) 3 weeks of entinostat monotherapy converts TIL/TAL-absent melanomas to TIL/TAL-present by histopathologic (H&E stain) analysis, (b) 3 weeks of single-agent entinostat induces changes in gene expression profiling by assessing distinct signatures as defined by RNA-sequencing signatures (RNA-seq; ‘immune-high’, innate anti-PD-1 resistance [IPRES], and epigenetic¹⁻³), (c) 3 weeks of single-agent entinostat induces changes in histone-accessible DNA by performing formaldehyde-assisted isolation of regulatory elements (FAIRE)⁴, (d) conversion of non-inflamed to inflamed melanomas by single-agent entinostat and/or antitumor response to the entinostat-pembrolizumab combination is associated with a baseline signature that consists of distinct somatic mutation gene profile, global histone modification profile in melanoma tissue or peripheral blood mononuclear cells (PBMC), and/or abundance of entinostat targets in melanoma cells (HDAC 1, 2, 3, and 11). Up to 12 evaluable patients will be treated with entinostat plus pembrolizumab for up to 27 weeks (approximately 6 months) based on clinical benefit. Patients who continue to have clinical benefit at 27 weeks may continue therapy with pembrolizumab or any other PD-1/PD-L1 inhibitor, as per standard of care.

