9.1.1 Definitions

Evaluable patients are those who complete all activities by at least day 22, namely: (a) they have received at least one and up to 4 entinostat weekly doses on day 1 and day 8, 15 and 22 (b) they have received the first pembrolizumab infusion on day 22 (± 2 days), and (c) they have completed day 22 (± 2 days) mandatory tumor biopsy. The rationale for this is to answer the primary translational endpoint regarding entinostat-alone immunomodulatory effects in peripheral blood and tumor tissue with sufficient power.

- SAE are events that meet FDA's definition as defined in [section 8.1.4](#) of the protocol irrespective of attribution to study drug(s). Subjects who receive at least one dose of entinostat are evaluable for safety.

- ORR by RECIST 1.1 criteria is the sum of complete response and partial response.

- PFS is measured from the date of enrollment on study to the date of documented progression. The rate of patients who are progression-free will be specifically calculated at 27-weeks (approximately 6 months) from study entry.

- OS is measured from the date of enrollment on study to the recorded date of death. The rate of patients who are alive at 27-week (approximately 6 months) will be specifically calculated for the study.

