9.2 Sample Size, Accrual and Duration of Accrual

Our goal is to enroll at least 10 evaluable patients. The immune-mediated mechanism of action of entinostat alone (primary translational endpoint) will be evaluated on representative H&E-stained tissue sections from tumor tissues collected at baseline and on day 22 by standard pathology analysis. This analysis will be conducted by [name], study pathologist. Density of TIL/TALs in these H&E-stained sections will be scored as a 0, 1+ (non-brisk), 2+ (brisk) ordinal variable¹⁵¹. By definition, upon enrollment if TILs are present based on H&E stained sections, they must be $\leq 1\%$ of the total number of cells in the specimen. A non-inflamed melanoma may have been ‘successfully’ converted to an inflamed melanoma following 21 days of entinostat ‘priming’ if the histopathologic analysis of day 22 melanoma biopsies shows any (i.e. brisk or non-brisk) evidence of TIL/TAL. In other words, we will capture the incidence of conversion as a dichotomous variable, present (i.e. brisk or non-brisk) or absent. Twenty-one days of entinostat ‘priming’ would be considered to have an immunomodulatory effect if at least 3 out of 10 evaluable patients show conversion of their melanomas from ‘non-inflamed’ to ‘inflamed’. This test has a type I error rate of 0.04 if the true rate is 0.08 and power of 83% if the true rate is 0.4.

The secondary endpoint is antitumor response by RECIST 1.1. Given that one of the determinants of response to single-agent PD-1 inhibitors is pre-existing TIL/TAL²⁹, we postulate that patients with metastatic melanoma and zero TIL/TAL will have nearly zero response rate. With 10 patients the exact 95% confidence interval for response rate is (0, 0.31) if 0 responses are observed out of 10 patients, and (0, 0.45) if 1 response is observed out of 10 patients.

Assuming that 20% of patients will not be evaluable due to screen failure, toxicity or rapid disease progression, and another 30% of enrolled patients will not have interpretable tumor biopsies on day 22 due to necrosis, stromal contamination or overall low quality, the total number of enrolled patients should be set to 14.

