10.3 Registration Procedures

All patients must be registered with the CPO at the UNC-CH before enrollment to study. Prior to registration, eligibility criteria must be confirmed with the UNC-CH Study Coordinator. To register a patient, call the CPO at [contact] Monday-Friday 9:00 am – 5:00 pm EST or email the UNC Project Manager.

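### Enrolment of 14 does not cover the losses assumed in Section 9.2: about 7 to 8 readable day-22 biopsies are expected (at most 9.8), while the stated 83% power needs 10 and no other cut-off is given

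*Combined protocol and SAP*

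**What the plan says.** Section 9.2 declares an immunomodulatory effect if "at least 3 out of 10 evaluable patients show conversion of their melanomas", and gives this rule a "type I error rate of 0.04 if the true rate is 0.08 and power of 83% if the true rate is 0.4". The enrolment figure comes at the end of the section. The plan assumes that "20% of patients will not be evaluable due to screen failure, toxicity or rapid disease progression" and that "another 30% of enrolled patients will not have interpretable tumor biopsies on day 22", and from these two assumptions concludes that "the total number of enrolled patients should be set to 14".

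Three other places bear on this:

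- Section 9.1.1 defines who is evaluable. On the biopsy, it asks only that "they have completed day 22 (± 2 days) mandatory tumor biopsy"; it does not ask that the sample be readable.
- Section 10.3 says "Prior to registration, eligibility criteria must be confirmed with the UNC-CH Study Coordinator", so some screen failures may fall outside the enrolled count.
- Section 1.1 describes the trial as an "exploratory (n=10-12 evaluable patients), open-label, single-arm, phase II study", a range rather than a single number.

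The visible text gives no replacement rule, no cut-off for any number other than 10, and no statement of how an uninterpretable biopsy enters the 3-of-10 count. Parts of Section 9.3 are redacted; Section 9.2, where the rule is stated, is not.

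**The concern.** The two loss assumptions and the enrolment total stand in one sentence and do not agree. The 30% is expressly additional to the 20%, so about half of those enrolled are expected to contribute nothing to the primary endpoint, yet the total exceeds 10 by only 4. The figure 14 is close to 10/0.70 = 14.3, as if only the biopsy loss had been allowed for. That is an inference; the plan does not show its derivation.

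This is the only test for which the visible text states an error rate and power. If it runs on 7 or 8 readable biopsies, failing to see 3 conversions is much weaker evidence against an effect than the quoted 83% suggests. A reader who relies on Section 9.2 would not know that. And because the rule is defined only at n = 10, the criterion for any other count would have to be chosen after the count is known, and possibly after the conversions are known too.

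**Working it through.** **Inputs.** From Section 9.2: cut-off 3 of 10, null rate 0.08, alternative 0.40, losses 20% and 30%, enrolment 14. From Section 1.1: 10 to 12 evaluable. All probabilities are exact binomial.

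**1. The plan's own test figures.**
- P(X ≥ 3 | n = 10, 0.08) = 0.0401, stated as 0.04.
- P(X ≥ 3 | n = 10, 0.40) = 0.8327, stated as 83%.

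Both reproduce, for exactly 10 assessable patients.

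**2. Enrolment needed to expect 10 assessable.**
- Losses add: 10 / (1 − 0.20 − 0.30) = 20.
- Losses compound: 10 / (0.8 × 0.7) = 17.9, so 18.
- 30% only: 10 / 0.70 = 14.3, so 15.

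The stated 14 is not reproduced.

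**3. What 14 delivers.** Let p be the chance that an enrolled patient has an assessable endpoint. Power is averaged over the assessable count m: Σ P(Bin(14, p) = m) × P(Bin(m, 0.4) ≥ 3). The last column caps m at 10, as if only the first 10 assessable were tested.

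| Reading of the 20% | p | 14p | P(m ≥ 10) | Power | Power, first 10 only |
|---|---|---|---|---|---|
| Adds to the 30% | 0.50 | 7.0 | 9% | 55% | 55% |
| Compounds with the 30% | 0.8 × 0.7 = 0.56 | 7.8 | 19% | 64% | 63% |
| Half is screen failure before enrolment | 0.9 × 0.7 = 0.63 | 8.8 | 36% | 72% | 71% |
| All is screen failure before enrolment | 0.70 | 9.8 | 58% | 80% | 77% |

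The half split in row three is an assumption for illustration; the plan gives no split. Row four is an upper bound, since the 20% also covers toxicity and rapid progression.

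**4. If accrual stops at 10 evaluable under Section 9.1.1.** Of 14 enrolled, 14 × 0.8 = 11.2 would be evaluable in that sense. The readable share among them is 0.70 (compounded, or all of the 20% screen failure) or (11.2 − 4.2)/11.2 = 0.625 (additive). Ten such patients give 7.0 or 6.25 readable biopsies. Power is P(Bin(10, 0.4 × 0.70) ≥ 3) = 56% or P(Bin(10, 0.4 × 0.625) ≥ 3) = 47%. With the cut-off held at 3, this is the same whether unreadable biopsies are excluded or counted as not converted.

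**5. The rule away from n = 10.**

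| n | Cut-off | Type I error at 0.08 | Power at 0.40 |
|---|---|---|---|
| 7 | ≥ 3 | 0.014 | 58% |
| 8 | ≥ 3 | 0.021 | 68% |
| 9 | ≥ 3 | 0.030 | 77% |
| 11 | ≥ 3 | 0.052 | 88% |
| 11 | ≥ 4 | 0.009 | 70% |
| 12 | ≥ 3 | 0.065 | 92% |
| 12 | ≥ 4 | 0.012 | 77% |

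At 11 or 12, keeping 3 exceeds the stated 0.04, and moving to 4 takes power below 83%.

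**The case against.** The strongest reply is that 7 to 8 is the pessimistic end. Section 9.2 names screen failure first among the causes of the 20%, and Section 10.3 has eligibility confirmed before registration, so some of that 20% may never be among the 14. The two percentages also have different denominators: one is of patients, the other of enrolled patients. This stands as far as it goes: the split is unstated, and 7.0 and 7.8 hold only if none of the 20% falls before enrolment. It does not rescue 14, because removing the whole 20% still gives 9.8.

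A second reply is that the stated goal is 10 *evaluable* patients as Section 9.1.1 defines them. On that count, 14 × 0.8 = 11.2 meets the goal, with an 87% chance of at least 10. But the endpoint is a histological reading, and a biopsy that cannot be read cannot be scored as converted or not. Section 9.2 raises unreadable biopsies in the sentence that sets 14, so it meant to allow for them.

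Third, a goal worded as a minimum might mean enrolling until 10 are reached. No such rule is visible and the total is fixed at 14, so the power figures are conditional on stopping there.

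Finally, the study is exploratory, and the inflation of type I error at 11 or 12 is modest. That is true, but the plan still states a decision rule, an error rate and a power, and they should describe the trial as planned.

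**Conclusion.** The concern holds. The test figures in Section 9.2 are right for exactly 10 assessable patients, but the enrolment figure does not follow from the plan's own loss assumptions. Fourteen enrolled gives an expected 7.0 to 7.8 assessable patients if none of the 20% is screen failure before enrolment, and no more than 9.8 on the most favourable reading. If accrual stops at 14 and the cut-off stays at 3, average power at a true rate of 0.40 is 55% to 64%, with a ceiling of 80%, against the stated 83%. These figures take the stated percentages at face value and treat patients as independent.

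Two gaps make it worse: evaluable does not mean readable, and no cut-off is given for a count other than 10, although the synopsis allows up to 12 and the plan's own assumptions make a shortfall likely. The statement about missing cut-offs applies to the visible text.

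**What to change.** Amend Section 9.2 as follows.

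1. Define *assessable for the primary endpoint* as having an interpretable day-22 biopsy, distinct from evaluable in Section 9.1.1. Use it as the denominator of the 3-of-10 rule, and say how uninterpretable biopsies are reported.
2. State how much of the 20% is screen failure before enrolment, and give the expected assessable number and power that 14 delivers (about 7 to 8 and 55% to 64% if none of it is). Note that 18 (compounded) to 20 (additive) enrolled would be needed to expect 10.
3. State that the test uses the first 10 assessable patients in order of enrolment, with any further patients reported descriptively.
4. Tabulate the rule for a shortfall. The cut-offs below are the smallest whose type I error does not exceed that of the n = 10 rule:

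| Assessable n | Cut-off | Type I error at 0.08 | Power at 0.40 |
|---|---|---|---|
| 10 | ≥ 3 | 0.040 | 83% |
| 9 | ≥ 3 | 0.030 | 77% |
| 8 | ≥ 3 | 0.021 | 68% |
| 7 | ≥ 3 | 0.014 | 58% |
| 6 | ≥ 3 | 0.009 | 46% |
| 5 | ≥ 3 | 0.005 | 32% |
| 4 | ≥ 2 | 0.034 | 52% |

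The higher power at 4 than at 5 or 6 comes from the discreteness of the binomial: a cut-off of 2 has type I error 0.054 at n = 5.

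The cost is one paragraph and a small table, and a less favourable stated power. No extra patients are needed if 14 is kept and the power restated. Choosing 18 to 20 would mean 4 to 6 more enrolled patients, each facing a mandatory biopsy; that is optional.

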9.3 Data Analysis Plans

Tumor response and AE of the entinostat-pembrolizumab combination will be tabulated and 95% confidence interval will be computed. PFS and OS will be estimated using Kaplan Meier method.

[REDACTED] The tumor imaging at baseline and on day 22, the peripheral blood assessment, and the baseline assessments for targeted mutation panel sequencing (FoundationOne®, or other targeted panel sequencing commercially available panel) are secondary correlative endpoints.

9.3.1 RNA sequencing (RNAseq)

Following macrodissection of tumor-enriched areas from tissue slides, [REDACTED] from baseline and day 22 tumor biopsy data will be processed, filtered, and aligned and transcript abundance quantitated, as previously described by [REDACTED]¹⁵⁶. The following parameters will be studied in these paired biopsies:

(A) Determination of molecular subtypes and relative expression of gene signatures associated with immune cellular and functional phenotypes from [REDACTED]¹⁶⁰

[REDACTED]

(B) [REDACTED]

(C) [REDACTED]

(D) [REDACTED]

[REDACTED]

The Kruskal-Wallis test with Dunn's post-tests will be used to compare clonal diversity and sharing of specific sequence motifs between baseline day 22 entinostat-alone priming. Given that these patients will have zero TIL/TAL at baseline, we anticipate that such analysis may be more informative on the day 22 tumor biopsies. In particular, *we anticipate tha*

[REDACTED]

9.3.2 Formaldehyde Assisted Isolation of Regulatory Elements (FAIRE)

Following deparaffinization and rehydration of tumor-containing

[REDACTED]

9.3.3 FoundationOne® Testing (or other acceptable testing)

[REDACTED]

9.3.4 Tumor Imaging Analysis

Tumor tissues will be collected at baseline and day 22. For all tumor tissue studies, which are described at length in Section 1.7.2.3, quantitative computer imaging analysis will be applied using commercially available [REDACTED]

10.0 STUDY MANAGEMENT

10.1 Institutional Review Board (IRB) Approval and Consent

It is expected that the IRB will have the proper representation and function in accordance with federally mandated regulations. The IRB should approve the consent form and protocol.

In obtaining and documenting informed consent, the investigator should comply with the applicable regulatory requirement(s) and should adhere to Good Clinical Practice (GCP) and to ethical principles that have their origin in the Declaration of Helsinki.

Before recruitment and enrollment onto this study, the patient will be given a full explanation of the study and the opportunity to review the consent form. Each consent form must include all the relevant elements currently required by the FDA Regulations and local or state regulations. Once this essential information has been provided to the patient and the investigator is assured that the patient understands the implications of participating in the study, the patient will be asked to give consent to participate in the study by signing an IRB-approved consent form.

Prior to a patient's participation in the trial, the written informed consent form should be signed and personally dated by the patient and by the person who conducted the informed consent discussion.

10.2 Required Documentation

Before the study can be initiated at any site, the following documentation must be provided to the Clinical Protocol Office (CPO) at the UNC-CH.

- A copy of the official IRB approval letter for the protocol and informed consent
- IRB membership list
- CVs and medical licensure for the principal investigator and any sub-investigators who will be involved in the study.
- Form FDA 1572 appropriately filled out and signed with appropriate documentation
- Financial Disclosures
- CAP and CLIA Laboratory certification numbers and institution lab normal values
- Executed clinical research contract

10.3 Registration Procedures

All patients must be registered with the CPO at the UNC-CH before enrollment to study. Prior to registration, eligibility criteria must be confirmed with the UNC-CH Study Coordinator. To register a patient, call the CPO at [contact] Monday-Friday 9:00 am – 5:00 pm EST or email the UNC Project Manager.

10.4 Data Management and Monitoring/Auditing

The CPO of the UNC LCCC will serve as the coordinating center for this trial. Data will be collected through a web-based clinical research platform, OnCore[®]. All data will be collected and entered into OnCore[®] by research coordinators from UNC LCCC.

The sponsor will provide direct access to source data/documents for trial-related monitoring, audits, IRB/IEC review, and regulatory inspection. As an investigator-initiated study, this trial will also be audited by the LCCC compliance committee every six or twelve months.

The sponsor will provide direct access to source data/documents for trial-related monitoring, audits, IRB/IEC review, and regulatory inspection. As an investigator initiated study, this trial will also be audited by the Lineberger Cancer Center compliance committee every six or twelve months, depending on the participation of affiliate sites.

10.5 Adherence to the Protocol

Except for an emergency situation in which proper care for the protection, safety, and well-being of the study patient requires alternative treatment, the study shall be conducted exactly as described in the approved protocol.

10.5.1 Emergency Modifications

UNC investigators may implement a deviation from, or a change of, the protocol to eliminate an immediate hazard(s) to trial subjects without prior UNC or their respective institution's IRB/IEC approval/favorable opinion.

For any such emergency modification implemented, a UNC IRB modification form must be completed by UNC Research Personnel within five (5) business days of making the change.

10.5.2 Single Patient/Subject Exceptions

Eligibility single subject exceptions are not permitted for Lineberger Comprehensive Cancer Center Investigator-Initiated Trials under any circumstances. Other types of single-subject exceptions may be allowed if proper regulatory review has been completed in accordance with Lineberger Comprehensive Cancer Center's Single Subject Exceptions Policy.

10.5.3 Other Protocol Deviations/Violations

According to UNC's IRB, a protocol deviation is any unplanned variance from an IRB approved protocol that:

- Is generally noted or recognized after it occurs,
- Has no substantive effect on the risks to research participants,
- Has no substantive effect on the scientific integrity of the research plan or the value of the data collected,
- Did not result from willful or knowing misconduct on the part of the investigator(s).

An unplanned protocol variance is considered a violation if the variance meets any of the following criteria:

- Has harmed or increased the risk of harm to one or more research participants.
 - Has damaged the scientific integrity of the data collected for the study.
- Results from willful or knowing misconduct on the part of the investigator(s).
- Demonstrates serious or continuing noncompliance with federal regulations, State laws, or University policies.

If a deviation or violation occurs, please follow the guidelines below:

Protocol Deviations: UNC will record the deviation in OnCore[®], and report to any sponsor or data and safety monitoring committee in accordance with their policies. Deviations should be summarized and reported to the IRB at the time of continuing review.

Protocol Violations: Violations should be reported by UNC personnel within one (1) week of the investigator becoming aware of the event using the same IRB online mechanism used to report Unanticipated Problems.

Protocol Deviations: In the event a deviation from protocol procedures is identified, record the deviation in OnCore[®] and assess for risk of patient safety.

Unanticipated Problems:

Any events that meet the criteria for "Unanticipated Problems" as defined by UNC's IRB must be reported by the study personnel using the IRB's web-based reporting system.

10.6 Amendments to the Protocol

Should amendments to the protocol be required, the amendments will be originated and documented by the Principal Investigator at UNC. It should also be noted that when an amendment to the protocol substantially alters the study design or the potential risk to the patient, a revised consent form might be required.

The written amendment, and if required the amended consent form, must be sent to UNC's IRB for approval prior to implementation.

10.7 Record Retention

Study documentation includes all eCRFs, data correction forms or queries, source documents, Sponsor correspondence to Investigators, monitoring logs/letters, and regulatory documents (e.g., protocol and amendments, IRB correspondence and approval, signed patient consent forms).

Source documents include all recordings of observations or notations of clinical activities and all reports and records necessary for the evaluation and reconstruction of the clinical research study.

Government agency regulations and directives require that all study documentation pertaining to the conduct of a clinical trial must be retained by the study investigator. In the case of a study with a drug seeking regulatory approval and marketing, these documents shall be retained for at least two years after the last approval of marketing application in an International Conference on Harmonization (ICH) region. In all other cases, study documents should be kept on file until three years after the completion and final study report of this investigational study.

